## 2.2 Secondary objective(s)

Secondary objective(s)	Endpoints related to secondary objective(s)

 
To assess the impact of CMK389 on steroid use (mg days)
 
	
 
Difference in steroid usage for each arm of the study between baseline and end of treatment
 

 
To assess the impact of CMK389 on a composite index of pulmonary physiology and exercise capacity
 
	
 
Proportion of patients who deteriorate from baseline to Week 16, defined as: relative reduction in FVC ≥ 10% or relative reduction in FEV1 ≥ 10% or relative reduction of DLCO ≥ 15% or relative reduction of 6MWD ≥ 50 m
 

Secondary objective(s)	Endpoints related to secondary objective(s)

 
To explore the impact of CMK389 observed with [F]-fluorodeoxyglucose positron emission tomography/computed tomography ([F]-FDG-PET/CT) imaging
 
	
 
Change in [F]-FDG-PET/CT (SUVmax and SUVmean) from baseline and Week 16
 

 
To assess the pharmacokinetics of

	
 
Pharmacokinetic parameters (Cmax/End of

CMK389	infusion, Ctrough) of CMK389

 
To assess the safety and tolerability of

	
 
Adverse events, vital signs and routine safety

CMK389	laboratory results.

 
To assess the impact of CMK389 on pulmonary physiology
 
	• Change in forced expiratory volume in one second (FEV1) and diffusion capacity for carbon monoxide (DLCO) between baseline and Week 16

 
To assess the impact of CMK389 on

	
 
Change in 6-minute walk distance (6MWD)

exercise capacity	between baseline and Week 16

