## Run-in Epoch

[figure not shown]
A 6-week run-in epoch will commence on **Day -42**. First, eligible patients will discontinue methotrexate and azathioprine. Hydroxychloroguine will be allowed to continue as background therapy. Then, on **Day -28** (2 weeks after discontinuation of methotrexate or azathioprine), patients will undergo a full safety assessment, a "Clinical Status Evaluation (CSE)", and enter into a steroid (prednisone or equivalent; see Table 17-1-Appendix 3) titration algorithm. CSE will consist of a 6-minute walk test, spirometry assessments, and an assessment of dyspnea (Modified Medical Research Council [mMRC] breathlessness scale). The CSE serves as an additional safety evaluation and will serve to establish the patient's current clinical status (Clinical Status Determination [CSD]) as compared to their status at Day -42 (Figure 3-2). The CSE will be performed at each subsequent visit, prior to the titration of steroids, and the CSD will guide selection of the next dose of steroids (Figure 3-3). Steroid titration will continue through the run-in epoch: and steroid titration will also continue through the treatment epoch. Patients with CSD of "improved" or "stable" will decrease steroid dose by 1-step on the dosing scale (Figure 3-4). (Note: To prevent Addisonian crisis, steroids will not be tapered below a physiologic dose (2.5 mg/day); and steroid tapering will follow a very slow regimen, as per protocol – i.e., modest decreases in dose, no more frequent than every four weeks). Patients with CSD of "deteriorating" will be ineligible to continue the study (if "deteriorating" is determined during the run-in epoch); or they will increase their steroid dose by 1-step (if "deteriorating" is determined during the treatment epoch). [ $^{18}$ F]-FDG PET/CT will be performed prior to the first dose (**Day -2 (± 1**)) and again at the end of the treatment epoch (**Day 113**).

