# Figure 3-2 Clinical Status Evaluation (CSE) and Clinical Status Determination (CSD)

	Clinical Status Evaluation (CSE)											
D		Change since Day -42 (V101)										
Parameters	Better	Same	Worse									
6MWT	↑ 50m	$\Delta = \pm (<50) \mathrm{m}$	↓ 50m									
FVC	+10% relative $\Delta$	-15% < relative $\Delta$ < +10%	-15% relative $\Delta$									
FEV1	+10% relative $\Delta$	-15% < relative $\Delta$ < +10%	-15% relative $\Delta$									
MMRC dyspnea score	-1 point	No change	+1 point									

Clinical Status	Improved	Stable	Deteriorating
Determination	3 or more parameters	Does not meet criteria for	2 or more parameters "Worse"
(CSD)	"Better"	"Improved" or "Deteriorating"	or $\Delta$ MMRC is $\geq$ 2 points

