#### 11.4.2 Statistical model, hypothesis, and method of analysis

The change from baseline in percent predicted FVC will be analyzed using a Bayesian model for repeated measurements. The model will investigate effects for treatment by time (included as a class variable) interaction, baseline FVC by time interaction, prior sarcoidosis immunosuppressant therapy (stratification factor) and baseline prednisone dose. The correlation among the repeated measures collected on the same subject will be assessed via an unstructured covariance matrix. The stratification factor may be removed in case of strata with low sample sizes impacting on the convergence of the model.

Uninformative priors will be utilized to obtain the posterior estimates. Baseline is defined as Day 1.

The posterior probability that CMK389 is better than placebo in terms of change from baseline in percent predicted FVC at 16 weeks will be calculated. If it is at least 90%, it will be considered a sign of efficacy of CMK389 in this patient population.

The primary analysis will include all available data from patients in the PD analysis set with baseline and at least one post baseline assessment.

A supplementary analysis may be conducted including also FVC values collected after a change of the background therapy not based on the CSD algorithm.

Novartis	Confidential	Page 83
Amended Protocol Version v08 (Clean)		Protocol No. CCMK389X2201

If data permits, additional subgroup analysis of the primary endpoint will be conducted for the following three subgroups: increased, no change and decreased prednisone dose at week 16 compared to baseline.

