# 11.5 Analysis of secondary variable(s)

#### 11.5.1 Efficacy / Pharmacodynamics

Data from other secondary variables will be listed and summarized. Graphical representations over time will be presented. Models similar to the one described for the primary analyses will be carried-out to investigate treatment difference for the continuous variables collected at each visit of the treatment epoch. Pulmonary physiology scores will be analyzed via ANCOVA model for repeated measures, while the percentage of subjects that, at Week 16, deteriorate (defined as: relative reduction from baseline in FVC  $\geq 10\%$  or in FEV1  $\geq 10\%$  or in DLCO  $\geq 15\%$  or relative of 6MWD  $\geq 50$  m) and the percentage of subjects who increased the steroid dose at least one time during the treatment epoch, will be analyzed using logistic regression. This analysis will be carried out if at least 20% of the subjects will show a deterioration/increase of the steroid dose.

The [F]FDG-PET/CT imaging data will be analyzed to identify the maximum standardized uptake values in the following categories:

• A maximum of 10 focal nodal uptake regions (mediastinal, hilar)

Page 84

- A maximum of 10 focal regions of uptake in lung parenchyma •
- A maximum of 10 extra-thoracic focal uptake regions on the whole body scan ٠

F]FDG-PET/CT mean uptake in the reference tissue:

• A region of lung parenchyma, unaffected by focal lesion uptake

The mean of the SUVmax (resp. SUVmean) for each category will be taken to obtain one SUVmax value (resp. SUVmean) per patient / time point / category.

The mean percent change from baseline in SUVmax in the lymph nodes after 16 weeks of treatment will be analyzed using ANCOVA with baseline SUVmax and baseline steroid doses as covariates, and treatment and prior sarcoidosis immunosuppressant therapy as factors.

The same analysis as for the percent change from baseline in SUVmax in the lymph nodes will be performed for the percent change from baseline in SUVmax in the lung parenchyma and the extra-thoracic regions, where available. It will also be repeated for SUV mean in the parenchyma.

The correlation between changes from initial FDG-PET scan in SUVmax and changes from baseline in FVC, FEV1 and 6MWT distance will be assessed with graphical methods.

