6.2 Secondary objectives

6.2.1 Variables

Secondary variables for this study are:

- Steroid use (mg days): Change from baseline in steroid usage as determined by the investigator's decision (for any reason algorithm mediated or just related to an investigator's decision).
- - Dose for subjects dosed with Methylprednisolone steroid doses of 4, 6, 8, 10 mg will be multiplied by 1.25 to become Prednisolone equivalent.
- Composite index of pulmonary physiology and exercise capacity: Subject who deteriorates from baseline to each visit/Week 16, is defined as a subject with:
 - o relative reduction if FVC \geq 10%, or
 - o relative reduction if FEV1 \geq 10%, or

- o relative reduction of DLCO \geq 15%, or
- o relative reduction of 6MWD \geq 50 m.
- [18F]FDG-PET/CT: Percent change from baseline in SUVmax and SUVmean
- Pulmonary function tests: Change from baseline in FVC (L), FEV1 (L and % predicted), FEV1/FVC, PEF and DLCO (absolute values and % predicted). DLCO expressed as % predicted and adjusted for Hemoglobin will be derived by the vendor as described in: Graham et others 2017. A composite physiological index (CPI) will be derived too following this formula: CPI = 91 0.65*DLCO(%) 0.53*FVC(%) + 0.34*FEV1(%)
- 6MWD: Change from baseline in distance walked and for the distance saturation product. The latter will be derived as the product between the distance walked and lowest oxygen saturation (SpO2%) value observed during the test, that is to say the lowest of the values taken after 1,2,3,4,5,6 Minutes from the start of the test (Lettieri 2006).
- IL-18 and IL-18bp concentrations

The direction of benefit is as follows

- an increase in values is beneficial for: absolute FVC, FEV1, PEF, DLCO and 6MWD.
- A decrease in values is beneficial for: [18F]FDG-PET/CT (SUVmax and SUVmean).

[18F]FDG-PET/CT

The [18F]FDG-PET/CT imaging data will be analyzed by the vendor to identify the standardized uptake values in the following categories:

- A maximum of 10 focal nodal uptake regions (mediastinal, hilar)
- A maximum of 10 focal regions of uptake in lung parenchyma
- A maximum of 10 extra-thoracic focal uptake regions on the whole body scan

[18F]FDG-PET/CT mean uptake in the reference tissue:

- Lung parenchyma, unaffected by focal lesion uptake
- Ascending aorta blood pool

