6.2.3 Statistical model, assumptions and hypotheses

[¹⁸F]-FDG-PET/CT

The mean percent change from baseline in SUVmax in the nodules and lung parenchyma at week 16 will be analyzed using ANCOVA with baseline SUVmax and baseline steroid doses as covariates and treatment and prior sarcoidosis immunosuppressant therapy as factors.

The same analysis as for the percent change from baseline in mean SUVmax in the nodules and lung parenchyma will be performed for the percent change from baseline in SUVmax in extrathoracic regions, where available, at week 16. It will also be repeated for SUVmean in the three categories.

The same sensitivity and subgroup analyses as the primary may also be performed, if deemed necessary.

A bar chart plot of the percent change from baseline with the corresponding SE will be provided.

Composite index of pulmonary physiology and exercise capacity /steroid dose

A logistic regression model with baseline steroid doses as a covariate and treatment and prior sarcoidosis immunosuppressant therapy as factors, will be applied to patients showing at least a deterioration (as determined by Composite index of pulmonary physiology and exercise

capacity- section 6.2.1) during the treatment period and to patients with at least one steroid dose increase (for any reason - algorithm mediated or just related to an investigator's decision).

Bar chart plots representing the percentage of patients with at least a deterioration during the course of the trial/ with at least one steroid increase during the course of the trial will be provided by treatment.

Key Pulmonary function tests and 6MWD

FVC (in litres), FEV1, FEV1/FVC, PEF, DLCO, DLCO adjusted for hemoglobin, CPI, 6MWD and distance saturation product changes from baseline will be analyzed using the same analysis as defined in Section 6.1.3 but under a frequentist approach (no prior will be applied). The same sensitivity and subgroup analyses as the primary may also be performed, if deemed necessary.

Model based means with corresponding standard errors (SE) by treatment and time will be used to visualize the results over time. A change from baseline of 0 will be assumed at baseline.

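### The logistic model for any steroid increase omits run-in lung-function change, a strong pre-randomisation predictor of the event; this costs some precision but does not bias the comparison

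*Protocol*

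**What the plan says.** - **Endpoint.** Protocol 2.2 lists steroid use in mg days: "Difference in steroid usage for each arm of the study between baseline and end of treatment". SAP 6.2.1 describes it as "Change from baseline in steroid usage as determined by" the investigator, whatever the reason for the change.
- **Baseline.** For the FVC model, protocol 11.4.2 says "Baseline is defined as Day 1". No separate baseline is given for steroid use.
- **Trigger.** Protocol 3.1 (Run-in Epoch) judges clinical status "as compared to their status at Day -42", and Figure 3-2 uses the same reference visit, V101. Protocol 8.5.5 applies the rule at V102, V201, V202, V203 and V204. In the treatment epoch a 'deteriorating' status raises the steroid dose by one step. That status needs two of four parameters 'Worse' (6MWT down 50 m, FVC down 15%, FEV1 down 15%, mMRC up 1), or an mMRC change of at least 2.
- **Entry filter.** Exclusion criterion 27 (protocol 4.2) removes patients already 'deteriorating' at Day -28 or Day 1.
- **Analysis.** Protocol 11.5.1 plans a logistic regression for "the percentage of subjects who increased the steroid dose at least one time during the treatment epoch", to be run if at least 20% of subjects show the event. SAP 6.2.3 specifies "A logistic regression model with baseline steroid doses as a covariate and treatment and prior sarcoidosis immunosuppressant therapy as factors" and counts increases for any reason. It does not repeat the 20% criterion.

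**The concern.** Methotrexate or azathioprine is stopped at Day -42, so the reference value for the trigger is taken before withdrawal. Any loss between Day -42 and Day 1 that stays short of the trigger is carried into the treatment epoch and uses up part of the margin to an increase. Two patients can both be randomised as 'stable' and yet need very different on-treatment losses to have the event.

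The model for that event contains no lung-function term. The primary FVC model adjusts for baseline FVC by time (SAP 6.1.3), the other lung-function and 6MWD models follow it, and the PET models adjust for baseline SUVmax (SAP 6.2.3). At stake are precision and readability. With about 28 patients per arm, the arms may by chance start at different distances from the trigger, and the planned model would not allow for that.

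**Working it through.** **1. The plan's own figure.** No power is given for the steroid analysis (protocol 11.8: not applicable). The only stated power is for FVC (protocol 11.7): 28 per arm, difference 5, SD 9, one-sided 10%. SE = 9 × √(2/28) = 2.405; 5/2.405 = 2.079; Φ(2.079 − 1.282) = 0.787, which agrees with the stated 80% or so. The same n and one-sided 10% level are used below.

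**2. Distance to the trigger (Figure 3-2 only, no assumptions).** FVC becomes 'Worse' at 0.85 of the Day -42 value. The on-treatment change needed is 0.85/(1 + run-in change) − 1.

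| Run-in FVC change | Calculation | Needed from Day 1 |
|---|---|---|
| +9% | 0.85/1.09 − 1 | −22.0% |
| 0% | 0.85/1.00 − 1 | −15.0% |
| −10% | 0.85/0.90 − 1 | −5.6% |
| −12.5% | 0.85/0.875 − 1 | −2.9% |
| −14% | 0.85/0.86 − 1 | −1.2% |

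FEV1 has the same threshold, and FVC and FEV1 crossing together are enough for an increase. If FVC and FEV1 alone have moved, every row can be randomised.

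**3. How strongly run-in change predicts an increase.** The documents give no noise or run-in SDs, so these are assumptions. Two separate simulations of the Figure 3-2 rules with no drug effect were run, the second with spirometry noise SD 3% to 5%, run-in mean 0 or −3% and run-in SD 5%.
- At least one increase after a run-in FVC loss of 10% or more: 36% to 51% in one, 33% to 43% in the other.
- At least one increase after a run-in gain above 5%: 6% to 8%, and 2% to 7%.
- Slope: −0.9 to −1.8 percentage points of risk per +1% run-in change. With no true run-in change it fell to −0.2.

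**4. Is the comparison biased?** A third simulation used spirometry noise SD 4%, 6MWD noise SD 20 m and run-in mean −5% (SD 5%), and removed patients 'deteriorating' at Day -28 or Day 1. With no treatment effect the two arms had increase rates of 38.9% and 39.1%. There is no systematic bias.

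**5. Dilution and precision.** Same simulation, with on-treatment FVC change by Day 85 of −4% on placebo and 0% on active (SD 5%), and large samples. The logistic model holds treatment alone, or treatment plus run-in FVC change.

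| Run-in mean (SD) | OR without | OR with | z without | z with | (z ratio)² |
|---|---|---|---|---|---|
| −5% (5%) | 0.478 | 0.443 | −57.9 | −60.5 | 1.09 |
| −5% (8%) | 0.513 | 0.452 | −50.3 | −54.2 | 1.16 |

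The covariate is thus worth roughly 9% to 16% more patients. Where power is 50% at one-sided 10%, the noncentrality is 1.282. Multiplying by the z ratios 1.045 and 1.078 gives Φ(0.058) = 0.52 and Φ(0.099) = 0.54. At trial size (n = 60) with Firth fits, simulated type I error stayed at or below 10% with and without the term, power rose by about 1 to 6 points, and the log odds ratio moved, for example, from −0.97 to −1.08.

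**6. Chance imbalance.** The simulated SD of run-in FVC change is 7.7% to 9.1%. Two standard errors of the arm difference are 2 × SD × √(2/28) = 4.1% to 4.9%. This moves the increase rates apart by 4.5 to 7 points. The SE of a difference in rates near 21% is √(2 × 0.21 × 0.79/28) = 10.9 points, so the shift is 0.4 to 0.6 SE.

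**The case against.** **The comparison is randomised.** Run-in change precedes randomisation, and the usual standard error already allows for chance imbalance in an omitted covariate. This stands. A reader might infer that pre-randomisation loss biases the steroid result; the equal null rates in step 4 show that it does not. What is left is the usual gain from adjusting for a strong predictor.

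**The listed endpoint is a different variable.** Protocol 2.2 concerns mg days, and a dose raised after Day 1 is real on-treatment use whatever triggered it. This also stands. A reader might see a contradiction between a Day 1 baseline and a Day -42 reference. There is none: one is the baseline for analysis, the other the reference for a clinical-status rule. SAP 6.2.3 gives no model for mg days, and the fix does not touch that endpoint.

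**The model may never run.** Protocol 11.5.1 requires 20% of subjects with the event. If the true rates were 20% to 22% on placebo and 9% to 10% on active, the pooled rate would be 14.5% to 16%. With 56 patients at least 12 events are needed (0.20 × 56 = 11.2), and the binomial chance is 10% to 18%. This limits the value of the fix. The rate depends on run-in loss, though: at a mean run-in loss of 5% the simulated pooled rate is (39.1% + 23.4%)/2 = 31%. Increases outside the algorithm would add to it.

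**It is partly covered.** Exclusion 27 caps the carried-over loss, and SAP 6.2.2 tabulates Better, Same and Worse by arm and visit. Those tables put −14% and +9% in the same category, and the FVC time points listed in SAP 6.1.1 omit Day -42. No continuous run-in change is planned.

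**Conclusion.** The point holds as a modest improvement to one secondary analysis in a non-confirmatory trial. The steroid-increase model leaves out a strong predictor that is fixed before randomisation and already measured. The cost is about 1 to 6 power points, some dilution of the odds ratio (for example 0.44 becoming 0.48), and chance imbalance left unadjusted.

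The distances to the trigger in step 2 follow from the protocol alone. All the simulated sizes rest on assumed noise, run-in change and treatment effect, and would shrink if little lung function changes during run-in. Increases made outside the algorithm are not tied to Day -42, which weakens the link further. A reader might also expect an FVC covariate to remove the dependence on run-in altogether. It would not, because the 6MWD and mMRC routes to the trigger remain unadjusted.

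**What to change.** In SAP 6.2.3, before unblinding:

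1. Add the relative change in FVC from V101 (Day -42) to V201 (Day 1) as one prespecified covariate in the logistic model for at least one steroid dose increase.
2. Fit that model with Firth penalisation, because events will be few.
3. Tabulate this continuous run-in change by arm beside the steroid results, so that the reader can see whether the arms started equally close to the trigger.

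The cost is SAP wording and one derived variable; Table 8-1 already schedules spirometry at both visits. The downside is one more parameter in a sparse-event secondary model that runs only if the 20% criterion in protocol 11.5.1 is met. The titration algorithm and the mg-days endpoint stay as they are.

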### 2.3 Exploratory objective(s)

[figure not shown]
Commercially Confidential Information

[figure not shown]
## 3 Investigational plan

#### 3.1 Study design

This is a subject and investigator blinded, randomized, placebo-controlled, parallel-group, repeat-dose, multicenter, non-confirmatory study of CMK389 in chronic pulmonary sarcoidosis. This study will investigate the safety and efficacy of 10 mg/kg CMK389 administered intravenously (i.v.) every 4 weeks for a total of 4 doses, versus placebo (Figure 3-1). After obtaining signed informed consent, a screening epoch of 28 days will be used to assess subject eligibility. The population will consist of patients with biopsy-proven pulmonary sarcoidosis, in Scadding stages II, III, or IV as determined by the most recent chest

x-ray. A high resolution computed tomography (HRCT) scan (historical or performed at screening (**Day -70 to -43**)) will be reviewed to select subjects with minimal fibrosis (< 15% reticular markings on a volumetric basis). Eligible patients must be treated with 5-15 mg daily prednisone (or equivalent) and methotrexate or azathioprine for  $\geq 6$  months prior to screening. Hydroxychloroquine is allowed as background therapy but not required. Approximately 66 subjects will be randomized in a 1:1 ratio to receive CMK389 or placebo. Randomization will be stratified by prior sarcoidosis immunosuppressant therapy (azathioprine or methotrexate).

## Run-in Epoch

[figure not shown]
A 6-week run-in epoch will commence on **Day -42**. First, eligible patients will discontinue methotrexate and azathioprine. Hydroxychloroguine will be allowed to continue as background therapy. Then, on **Day -28** (2 weeks after discontinuation of methotrexate or azathioprine), patients will undergo a full safety assessment, a "Clinical Status Evaluation (CSE)", and enter into a steroid (prednisone or equivalent; see Table 17-1-Appendix 3) titration algorithm. CSE will consist of a 6-minute walk test, spirometry assessments, and an assessment of dyspnea (Modified Medical Research Council [mMRC] breathlessness scale). The CSE serves as an additional safety evaluation and will serve to establish the patient's current clinical status (Clinical Status Determination [CSD]) as compared to their status at Day -42 (Figure 3-2). The CSE will be performed at each subsequent visit, prior to the titration of steroids, and the CSD will guide selection of the next dose of steroids (Figure 3-3). Steroid titration will continue through the run-in epoch: and steroid titration will also continue through the treatment epoch. Patients with CSD of "improved" or "stable" will decrease steroid dose by 1-step on the dosing scale (Figure 3-4). (Note: To prevent Addisonian crisis, steroids will not be tapered below a physiologic dose (2.5 mg/day); and steroid tapering will follow a very slow regimen, as per protocol – i.e., modest decreases in dose, no more frequent than every four weeks). Patients with CSD of "deteriorating" will be ineligible to continue the study (if "deteriorating" is determined during the run-in epoch); or they will increase their steroid dose by 1-step (if "deteriorating" is determined during the treatment epoch). [ $^{18}$ F]-FDG PET/CT will be performed prior to the first dose (**Day -2 (± 1**)) and again at the end of the treatment epoch (**Day 113**).

